9.3 POPULATIONS FOR ANALYSES

Led by the study statistician and PI, an intent-to-treat main analysis will use all available data from baseline onwards for patient and caregivers to examine effectiveness.

9.4 STATISTICAL ANALYSES

9.4.1 GENERAL APPROACH

Overall considerations. We will use an intention to treat approach for all analyses. That is, all participants will be included in their respective assigned conditions, regardless of their degree of participation in the study. [name] (Co-I; Statistician) and the data analyst will lead and conduct the analysis. The data analyst and project staff will perform data cleaning and validation throughout the study. Primary data analysis will begin with descriptive statistics for baseline characteristics and outcomes. We will examine balance between study groups with respect to baseline characteristics using effect sizes such as the standardized mean difference for numerical variables and Cramer's V for categorical variables. Conceptually relevant baseline factors showing non-trivial imbalances between groups will be then used as adjusting covariates in the longitudinal group comparisons. Distributional assumptions will be examined and, when appropriate, we will employ inferential and modeling

procedures robust to distributional assumptions such as normality. We will calculate and present means, variances, and ranges of the LSA and other secondary outcomes at baseline, 12 weeks, and 24 weeks. We will use the latest versions of SAS and R for all analyses and reports.

Handling of missing data. We will examine patterns of missing data, and whether baseline characteristics are associated with dropout. Conceptually relevant baseline factors predictive of dropout will then be used as adjusting covariates in the longitudinal group comparisons. Mixed-effect modeling techniques and covariate adjustment will reduce the impact of missing data, as the missingness is not assumed completely at random (MCAR) but conditionally (on the covariates) at random (i.e., MAR, a milder assumption).

9.4.2 ANALYSIS OF THE PRIMARY ENDPOINT(S)

We will summatively evaluate EPIC using the RE-AIM (Reach, Effectiveness, Adoption, Implementation, and Maintenance) evaluation framework.

Reach: We will use REDCap to track rates of screening, eligibility, enrollment, reasons for non-consent of eligible participants, and drop out.

“Effectiveness”: We will measure several secondary GeriPal outcomes and will explore participant perspectives on the acceptability and impact of EPIC as well as barriers and facilitators to implementation. The PI will train the project coordinator to conduct post-intervention semi-structured in-depth interviews of patients and their caregivers by telephone using an interview protocol developed during our pilot trial. The separate patient and caregiver interviews will be audio-recorded and transcribed using Landmark Associates. The PI will review every five transcripts for quality assurance to review with the coordinator and for ongoing interview guide refinement. We will conduct a thematic analysis of transcripts using NVivo Software (Version 12, QSR International). Informed by a within- and across- case comparison approach, we will code the data using concepts introduced by participants. Emerging codes across cases will be operationally defined and entered into a formal codebook. Member checking will be ongoing as previous participant insights will be asked of future participants (e.g. “A number of participants have said X. What is your perspective on this issue?”). To corroborate findings and establish trustworthiness, the PI and co-investigators will examine the data collection and analysis monthly and provide critical feedback on the emerging codes. We will explore within and across coded texts to extract converging themes and reach consensus on themes.

Adoption: We will record completion of intervention components (CYC sessions, follow up call, advance directive, activities) in REDCap and tabulate intervention completion rates (# participants completing component). Consistent with our prior intervention development studies, ≥80% completion rates for intervention sessions will be considered as evidence of feasibility.

Implementation: Informed by our prior fidelity monitoring procedures, we will audio record all palliative care coach intervention sessions for fidelity monitoring and will quarterly review at least 50% of the recordings to ensure standardized intervention delivery and further training.

Maintenance: The thematic analysis will explore barriers to maintenance, and nurse coaches assess maintenance of practices at the follow-up calls.

9.4.3 ANALYSIS OF THE SECONDARY ENDPOINT(S)

The statistician and the data analyst will lead and conduct the analysis, and the data analyst will perform data cleaning and validation throughout the study. Descriptive statistics for baseline characteristics will be presented and compared between study arms using t-test and chi-square as appropriate. The secondary geriatrics-palliative care outcome measures will be summarized by tabulating and plotting descriptive statistics (means, ranges, and variances) at baseline and at six months. All analyses will be performed by using SAS 9.4, and statistical significance will be defined at $\alpha<0.05$.

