3 AIMS AND OUTCOMES

TRIAL OUTCOMES - SUMMATIVE EVALUATION	
RE-AIM Implementation Framework (Aims 1 & 2)	
Reach Trial feasibility	Rates of screening, enrollment, retention, reasons for exclusion and refusals, randomization, and attrition.
Adoption Intervention feasibility	Mean rates of completion of core EPIC components out of possible 10 for patients and 8 for caregivers. Feasibility: Overall average completion of ≥8 sessions for patients ≥6 sessions for caregivers .
Acceptability	Quantitative (Patients/Caregivers): Post-intervention survey on intervention acceptability. Acceptability: Overall average score ≥8 of 10. Qualitative (Patients/Caregivers): Post-intervention semi-structured, in-depth interviews by telephone to explore acceptability, barriers, facilitators, and survey burden.
Implementation Intervention fidelity	A random sample of 50% of palliative nurse coach sessions will be reviewed monthly using a rigorous fidelity checklist. Palliative nurse coaches who exhibit a pattern of non-adherence on three consecutive ratings will receive additional supervision and training.
Survey completion	Quantitative: Survey completion rates. Feasibility: ≥80% of participants complete all surveys
Define usual care arm	Review electronic medical record to capture elements of “usual COPD care”.
Maintenance	Nurse coaches check in monthly to reinforce EPIC. Interviews explore barriers to maintenance.
“Effectiveness” (Exploratory Aim; Secondary Outcomes at Baseline, 12 weeks, and 24 weeks, where indicated)	
Life-Space Mobility (Target Secondary Outcome; R01 outcome)	UAB Life Space Assessment (LSA) (Patients/Caregivers): 15-item measure of community mobility; frequency, distance, and independence of movement in the 4 weeks prior to administration; LSA<60 (restricted Life-Space mobility) Lower scores → more restricted; MCID=5 points ($\alpha=0.80$).
Quality of Life	Chronic Respiratory Questionnaire (Patients): 20-item measure of quality of life in COPD; domains of dyspnea , fatigue , emotional function , and mastery . Higher scores → better. MCID=0.5 ($\alpha=0.70$) PROMIS Global Health 10 (Patients/Caregivers): 10-item measure; physical and mental health domains; 9 questions rated on a 5-point Likert-scale, and 10th question rates pain on a scale of 0 to 10. Raw scores converted to standardized t-scores ranging from 0 to 100, with lower scores → worse QOL.

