9 STATISTICAL CONSIDERATIONS

9.1 HYPOTHESES

Aim 1: Explore feasibility and acceptability of the EPIC intervention.

Hypothesis 1. Participants can feasibly complete the EPIC intervention (>80% of intervention components completed) and report high acceptability (*primary outcome*).

Aim 2: Determine the feasibility of a hybrid-type 1 effectiveness-implementation trial in older adults with COPD and their caregivers.

Hypothesis 2. It is feasible and not burdensome to recruit, randomize, retain, and survey older adults with COPD and their caregivers (*primary outcome*).

Exploratory Aim: Explore mean and variance estimates on Life-Space mobility by the UAB Life Space Assessment and other GeriPal outcomes to inform a fully-powered trial (*secondary outcome*).

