The primary risks of study participation are a loss of confidentiality and the discomfort associated with discussing aspects of one's experience coping with advanced cancer. To address these concerns, [name] will train all project staff to recognize signs of distress and to be supportive and/or make alternative plans for completing study-related tasks at a later date, if necessary. If a participant exhibits suicidal ideation at any point, [name] and other key clinical members of the study team will be contacted immediately to implement a crisis intervention plan (see **Section 12.2** for Emotional Distress/Suicide Protocol).

Plans to Monitor Trial Performance (e.g., assure fidelity to protocol and integrity of data)

[name] and [name] have developed and utilized structured processes for ensuring fidelity in study protocols including: 1) core training and study-specific refresher course in standardized interviewing that includes role-playing and supervision; 2) weekly team meetings to troubleshoot recruitment and data collection issues; and, 3) use of data entry software that provides entry validation range tests and is designed to minimize missing data by flagging missed items before surveys are submitted.

A data analyst study team member will manually extract data from the medical record regarding patient participants' clinical characteristics of stage, treatment, and co-morbidities. To ensure accuracy, the analyst will audit a random 10% of the medical records to verify the accuracy of the abstracted

information. The study coordinator will maintain and monitor the database regularly throughout the study. The database is password-protected and sits behind the firewall of UAB.

Interim Analyses and Stopping Rules

Early Termination for Significant Risk or Injury. - This is unlikely due to the supportive, non-invasive nature of the intervention. However, we will summarize adverse event data annually to the SO for consideration of study continuation. The study design does not include planned interim analyses to identify the need to stop early due to significant benefit, i.e., inferential analyses will be conducted when data collection has been completed. However, primary outcome data will be summarized quarterly and presented to the SO to decide if an interim inferential analysis is warranted to determine whether the study should be terminated early due to relevant benefit.

Table 1. Study Risk Assessment *				SCORE
I. Experimental Treatment				

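### Section 9.4.3 plans only descriptive summaries of the exploratory secondary outcomes but sets a 0.05 threshold for all analyses, while 9.3 and 9.4.1 plan effectiveness comparisons with no testing order or lead contrast

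*Combined protocol and SAP*

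**What the plan says.** Several sections bear on how the secondary outcomes will be analysed.

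- **Section 9.1** sets the Exploratory Aim: "Explore mean and variance estimates on Life-Space mobility by the UAB Life Space Assessment and other GeriPal outcomes to inform a fully-powered trial". The Section 3 table uses the same label: "Exploratory Aim; Secondary Outcomes at Baseline, 12 weeks, and 24 weeks, where indicated".
- **Section 3** marks the LSA as the target secondary outcome and the outcome for the later R01. It is collected in patients and in caregivers.
- **Section 9.3** says that "an intent-to-treat main analysis will use all available data from baseline onwards for patient and caregivers to examine effectiveness".
- **Section 9.4.1** plans mixed-effect models and adjustment: "Conceptually relevant baseline factors showing non-trivial imbalances between groups will be then used as adjusting covariates in the longitudinal group comparisons". It also presents the outcomes at baseline, 12 weeks and 24 weeks.
- **Section 9.4.3** limits the secondary outcomes to tabulated and plotted means, ranges and variances at baseline and six months. The only tests it names, the t-test and chi-square, are for baseline characteristics. It then closes with "All analyses will be performed by using SAS 9.4, and statistical significance will be defined at" 0.05.
- **Section 10.1.7**, explaining why no interim efficacy look is planned, adds that "inferential analyses will be conducted when data collection has been completed".

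No section lists the tests, the contrast or visit to be tested, an order of testing, or how multiplicity is to be treated. Section 9.4.9 (exploratory analyses) is marked not applicable.

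**The concern.** The aim and the main sentence of Section 9.4.3 are descriptive. Sections 9.3 and 9.4.1 go further, and the threshold in 9.4.3 covers every analysis without exception. An analyst following the text could compare the arms on every secondary score, in both populations and at either follow-up, and call any p-value below 0.05 significant.

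Two things are at stake. First, with many unranked comparisons a chance finding is a real prospect. Second, the trial is sized for precision, not for detecting differences, so a difference large enough to reach significance would greatly overstate a true effect of the size the protocol calls important. Either could be read as evidence that EPIC works, or could influence the planning of the larger trial that this pilot is meant to inform.

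**Working it through.** **1. The plan's own figure.** Section 9.2 gives a margin of error of 14.3 points for mean LSA with 12 patients per arm and SD 25.2. Half-width = 1.96 × 25.2 / √12 = 14.26, which rounds to 14.3, and 14.3 / 25.2 = 0.567 SD. It reproduces. It is the precision of a single-arm mean, not of a difference between arms.

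**2. Which text governs a between-arm outcome comparison?**

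| Section | Nature of analysis | Time points |
|---|---|---|
| 9.1 | Exploratory means and variances | Not given |
| 9.3 | Main analysis, effectiveness purpose | Baseline onwards |
| 9.4.1 | Summaries, plus adjusted longitudinal group comparisons | Baseline, 12 and 24 weeks (summaries) |
| 9.4.3 | Summaries, plus a 0.05 threshold for all analyses | Baseline and six months |

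The comparisons in 9.4.1 cannot be the baseline balance checks, because baseline imbalances enter them as covariates. So outcome comparisons are planned, and only 9.4.3 supplies a decision rule for them.

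**3. How many scores?** From the schedule in Section 1.4 and the domains in Section 3:

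- Patients: LSA 1, CRQ 4, PROMIS 2, HADS 2, mTICS 1, loneliness 1, Katz 1, Lawton 1 = 13.
- Caregivers: LSA 1, PROMIS 2, HADS 2, loneliness 1, Katz 1, Lawton 1, burden 3 = 11.

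Total 24. It is 25 if caregivers also complete the mTICS, which Section 3 says and Section 1.4 does not. Palliative care uptake is left out. Counting by domain is an assumption.

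**4. Chance of at least one false positive**, with no true effects and each test two-sided at 0.05. Sidedness is not stated, so two-sided is assumed. For k independent tests this is 1 − 0.95^k; for 24 tests, 1 − 0.95^24 = 0.708. For test statistics with a common correlation, the probability that none is significant is integrated over a shared normal factor. The documents give no correlations, so a range is shown.

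| Tests | Correlation 0 | 0.5 | 0.7 |
|---|---|---|---|
| LSA only: 2 populations × 2 visits = 4 | 0.185 | 0.156 | 0.130 |
| 24 scores, one test each | 0.708 | 0.458 | 0.311 |
| 24 scores × 2 visits = 48 | 0.915 | 0.613 | 0.399 |

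The chance stays above one half up to a correlation of about 0.4 for 24 tests (0.529 at 0.4) and about 0.6 for 48 tests (0.506 at 0.6). A simulation with more structure (within-person correlation 0.2 to 0.7, patient–caregiver 0.1 to 0.2, between-visit 0.6 to 0.8) gives 67% down to 41% for 24 tests and 86% down to 55% for 48.

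**5. What a significant LSA result would mean.** Inputs: SD 25.2 and 12 per arm (Section 9.2); MCID 5 points (Section 3).

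- Standard error of the difference = 25.2 × √(2/12) = 10.29.
- Critical t on 22 degrees of freedom = 2.074.
- Smallest significant difference = 2.074 × 10.29 = 21.3 points, or 21.3 / 5 = 4.3 times the MCID.
- Noncentrality at a true 5-point difference = 5 / 10.29 = 0.49; power from the noncentral t = 7.5%.
- By simulation at that true difference, significant estimates average about 4.8 times the truth in absolute size, and about 10% have the wrong sign.

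Two checks on sensitivity:

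- With all 15 per arm retained, the threshold is 2.048 × 25.2 × √(2/15) = 18.8 points.
- With baseline adjustment at an assumed correlation of 0.7 and 12 per arm, the residual SD is 25.2 × √(1 − 0.49) = 18.0. The threshold is 2.080 × 18.0 × √(2/12) = 15.3 points, with power about 10%.

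**The case against.** The strongest reply is that Section 9.4.3 already does what an exploratory aim calls for. It plans description, names tests only for baseline characteristics, and its 0.05 sentence can be read as a software-and-threshold line for those tests. In addition, Section 9.1 carries the exploratory label inside the statistical chapter, LSA is already singled out, Section 9.2 justifies the size by precision in patients, and a pilot does not need multiplicity adjustment. The Section 10.1.7 phrase concerns timing and names no secondary outcome. The LSA threshold in the working is for an unadjusted comparison, whereas the plan foresees adjusted mixed models.

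Much of this stands, and it rules out stronger readings that a reader might infer:

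- *That about 24 scores are each tested at two follow-ups.* No section says so. A mixed model could yield one group-by-time test per outcome, and domain scores might not be tested separately.
- *That a chance significant result is more likely than not.* This depends on the number of tests and on correlations the documents do not give. With one test per score and a common correlation of 0.5, the figure is 0.46.
- *That the exploratory label is missing from the statistical section because 9.4.9 is not applicable.* Section 9.1 carries it.
- *That there is no priority among outcomes.* LSA has priority. What is missing is a testing order and a named population and visit.
- *That the plan wrongly claims power for the MCID.* It claims none.

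The reply does not remove the conflict. If only description is intended, the effectiveness purpose in 9.3 and the group comparisons in 9.4.1 say otherwise. If comparisons are intended, a threshold worded to cover all analyses applies to them. Adjustment lowers the LSA threshold, but under the assumption shown it remains about three times the MCID (15.3 / 5 = 3.1).

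**Conclusion.** The point holds as an inconsistency that leaves room for misleading significance claims. Sections 9.1 and 9.4.3 treat the secondary outcomes as exploratory and descriptive; 9.3, 9.4.1 and the threshold in 9.4.3 together allow between-arm testing, with no testing order and no lead contrast.

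The false-positive risk cannot be fixed at one number. It is about 31% to 71% with one test per score, about 40% to 91% with both follow-ups tested, and about 13% to 19% for LSA alone across two populations and two visits. These ranges assume two-sided tests, no true effects, and a common correlation between 0.7 and 0; the first two also assume 24 scores.

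The LSA result does not depend on the test count. At the plan's SD and evaluable size, an unadjusted difference needs about 21 points against an MCID of 5, with power about 7.5%, so a significant result would greatly overstate any MCID-sized effect. Leaving exploratory pilot outcomes unadjusted for multiplicity is not itself a fault; the significance language is. The change is worth making because it is cheap and brings the analysis into line with the stated aim.

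**What to change.** - **Section 9.4.3:** limit the 0.05 threshold so that it does not apply to between-arm comparisons of secondary outcomes. State that these are exploratory, reported as estimates with 95% confidence intervals and without significance claims.
- **Section 9.3:** give the purpose of the main analysis as estimating means, variances and between-arm differences.
- **Sections 9.4.1 and 9.4.3:** use the same time points in both.
- **Lead estimate:** name one patient LSA contrast as the lead estimate for the R01, with all other outcomes, populations and visits as supporting. Week 24 would fit the six-month summary in 9.4.3, but the documents do not dictate that choice.
- **Sections 1.4 and 3:** while editing, reconcile whether caregivers complete the mTICS.

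The cost is protocol and SAP wording only. The downside is that the sponsor gives up the option of calling a secondary result significant.

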9.4.4 SAFETY ANALYSES

N/A

9.4.5 BASELINE DESCRIPTIVE STATISTICS

Intervention groups will be compared on baseline characteristics (e.g., demographics, baseline questionnaire values) using descriptive statistics.

9.4.6 PLANNED INTERIM ANALYSES

N/A

9.4.7 SUB-GROUP ANALYSES

N/A

9.4.8 TABULATION OF INDIVIDUAL PARTICIPANT DATA

Individual participant data will not be listed by measure and time point.

9.4.9 EXPLORATORY ANALYSES

N/A

10 SUPPORTING DOCUMENTATION AND OPERATIONAL CONSIDERATIONS

10.1 REGULATORY, ETHICAL, AND STUDY OVERSIGHT CONSIDERATIONS

10.1.1 SCREENING AND RECRUITMENT

Given ongoing constraints of the COVID-19 pandemic, all attempts will be made to recruit and consent participants virtually to maintain patient and study staff safety. We have submitted a HIPAA waiver to screen the electronic medical record to identify potentially eligible patient participants. The PI, study coordinator, and study staff will daily screen potentially eligible patient participants from the list of patients who have a planned visit in pulmonary clinics in the next 1-2 weeks. These procedures have been used successfully in recruiting patients with COPD in prior UAB studies.

Prior to recruitment, the PI will reach out to individual UAB pulmonologists by email to describe the study, to discuss recruitment of their patients, and to allow them to opt-out of recruitment. The PI has ready access to the clinic lists of all patients seen in both pulmonary clinics as part of routine clinical care.

After gaining permission from the patient's attending pulmonologists via the above opt out email, the PI, study coordinator, and study staff will screen electronic medical records in the UAB IMPACT system to identify potential participants from their list of patients who meet the inclusion criteria and have a planned office visit at the pulmonary clinic in the next 1-2 weeks. The PI or study coordinator will send potentially eligible patient participants a study information and opt-out letter by mail (included in the appendix) with details about the study and consent forms to introduce the study and let them know that a member of the study team will be contacting them by phone to talk to them about the study.

Individuals will be given a number to call if they do not wish to be contacted further for the study. The PI or study staff will call patients 5 business days after the opt out letter is sent to introduce, enroll, and consent them to the study.

At the time of the recruitment phone call, the PI or study coordinator will inform the patient about the study, answer any questions, and invite those interested and eligible to participate. Patient participants will be screened at this time for eligibility, and agreeable and eligible patient participants will complete consent. The study coordinator will confirm with the patient that they have a caregiver defined as, "a person who knows you [the patient] well and is involved in your medical care". The study coordinator will then ask permission from the patient to inform the caregiver about the study, and if agreeable, will screen the caregiver for eligibility criteria and perform consent in a similar fashion.

